### CONFIDENTIAL

This document is a confidential communication of Consumer Product Testing Company, Inc. containing Testing Facility capabilities and processes, and as such, is intended solely for the use of the Sponsor and Testing Facility in the performance of services. The confidential information contained herein, shall only be released by either Party upon compelled disclosure in compliance with legal or regulatory requirement.

valid results from a maximum of 25 subjects, then the test shall be rejected. For details on the sequential procedure and calculations, see reference 12.1.

Subjects who meet all of the inclusion criteria (Section 5.2) and none of the exclusion criteria (Section 5.3) will qualify for trial participation. Subjects cannot all be of the same skin phototype.

## 5.2 Inclusion Criteria

1. Subject must read and execute an informed consent document (that includes a HIPAA statement) indicating that the subject has been informed of all pertinent aspects of the trial before any assessment is performed;
2. Subject must be 18 to 70 years of age inclusive, at the signing of the informed consent;
3. Subject must complete a Medical History Form (MHF) prior to their trial initiation;
4. Subject must be willing and able to comply with scheduled visits, treatment plan, laboratory tests, and other trial procedures;
5. Subject must agree not to expose their back to additional sunlight or tanning beds, as either can alter the test results;
6. Subject must agree not to apply any topical skin-care product to the test sites during this trial;
7. Male or female subjects of childbearing potential must agree to use a highly effective method of contraception throughout the trial and for 14 days after the last application of assigned treatment. A subject is of childbearing potential if, in the opinion of the investigator, he/she is biologically capable of having children and is sexually active;
8. Female subjects of childbearing potential must be willing to comply with urine pregnancy testing requirements prior to initiation of trial testing procedures and as may be required for the duration of the trial;
9. Subject must be considered dependable and capable of understanding and following directions;
10. Subject must have self-perceived Fitzpatrick skin phototype I, II, or III:

Skin Phototype	Sunburn and Tanning History
I	Always burn easily; never tans
II	Always burns easily; tans minimally
III	Burns moderately; tans gradually; and

11. Subject must have an ITA° value >28°, determined by the Testing Facility by colorimetric methods, within 1 week of trial participation.

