### 5.3 Exclusion Criteria

1. Subject is in ill health as determined by the Principal Investigator;
2. Subject is an employee of the Clinical Division of the investigational site or a member of their immediate family;
3. Subject is a GSK CH employee directly involved in the conduct of the trial or a member of their immediate family;
4. Female subject is pregnant or intending to become pregnant over the duration of the trial or any female subject of childbearing potential who fails to produce a negative urine pregnancy test;
5. Female subject who is lactating (self-reported);
6. Subject using medication with photo-sensitizing potential;
7. Subject has a history of adverse reactions or hypersensitivity to azo dyes, cosmetics, OTC drugs, or other topical personal care products;
8. Subject taking medications other than birth control that could influence the purpose, integrity or outcome of the trial;
9. Subject has used topical or systemic steroids, antihistamines, or antibiotics within 7 days of trial initiation or during the trial;
10. Subject has used anti-inflammatory medications within 7 days of trial initiation or during the trial, that in the opinion of the PI, could interfere with the trial;
11. Subject has used medication suspected of causing photobiological reactions (e.g., tetracyclines, thiazides, etc.), that has not been taken by the subject through a summer season;
12. Subject has a dermatological condition;
13. Subject has a history of abnormal response to the sun, or a condition such as lupus erythematosus or skin cancer;
14. Subject uses tanning beds frequently;
15. Subject whose test site was exposed to sunlight within the previous 4 weeks;
16. Subject has a sunburn, suntan, uneven skin color, visible skin disease, scarring, or tattoo that would interfere with evaluation of test results;

Note: The presence of non-dysplastic nevi, blemishes, or moles will be acceptable if, in the PI's judgment, they will neither compromise the clinical trial, nor jeopardize a subject's safety. A subject with dysplastic nevi should be disqualified.

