### **5.4.2 Contraception**

All male subjects able to father children and female subjects who are of childbearing potential and are sexually active and at risk for pregnancy must agree to use a highly effective method of contraception consistently and correctly for the duration of the active trial period and for 14 days after the last dose of investigational product.

The investigator or his or her designee will discuss with the subject the need to use highly effective contraception consistently and correctly according to the schedule of activities and document such conversation. In addition, the investigator or his or her designee will instruct the subject to call immediately if the selected contraception method is discontinued or if pregnancy is known or suspected in the subject or the subject's partner.

The following is the all-inclusive list of the highly effective methods for avoiding pregnancy that meets the GSK definition (i.e., have a failure rate of less than 1% per year when used consistently and correctly and, when applicable, in accordance with the product label).

The list does not apply to females of reproductive potential with same sex partners or for subjects who are and will continue to be abstinent from penile-vaginal intercourse on a long term and persistent basis, when this is their preferred and usual lifestyle. Periodic abstinence (e.g., calendar, ovulation, symptothermal, post-ovulation methods) and withdrawal are not acceptable methods of contraception (reference 12.3).

1. Contraceptive subdermal implant
2. Intrauterine device or intrauterine system

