### CONFIDENTIAL

This document is a confidential communication of Consumer Product Testing Company, Inc. containing Testing Facility capabilities and processes, and as such, is intended solely for the use of the Sponsor and Testing Facility in the performance of services. The confidential information contained herein, shall only be released by either Party upon compelled disclosure in compliance with legal or regulatory requirement.

- For female subjects of childbearing potential, a urine pregnancy test will be administered, per the manufacturer’s instructions (subject urinates into paper cup, then inserts dipstick into urine per instructions, urine is dumped into toilet by subject) and test will be collected by laboratory staff. CPT staff will verify subject has disposed of urine. No urine is collected. Pregnancy test results will be noted on the Urine Pregnancy Test Results Log and the test dip stick will be disposed of in a waste receptacle. The urine pregnancy test will have a sensitivity of at least 25 mIU/mL. A negative pregnancy result is required before any test material is applied to the subject. Pregnancy tests may be repeated when potential pregnancy is suspected during participation in the trial (e.g., one menstrual cycle is missed during the testing period), as per request of the IRB, or if required by local regulations. In the case of a positive confirmed pregnancy, the subject will be withdrawn from the trial.

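### Inclusion 7 builds sexual activity into childbearing potential while Section 5.4.2 keeps the two apart, so a fertile woman judged not sexually active need not have a pregnancy test

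*Combined protocol and SAP*

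**What the plan says.** The only definition of the term is in Section 5.2, inclusion 7. A subject meets it if, in the investigator's opinion, "he/she is biologically capable of having children and is sexually active". The same item uses the term to set the contraception duty for men and women.

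Three provisions on baseline pregnancy testing then rely on it:

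- Section 5.2, inclusion 8: "Female subjects of childbearing potential must be willing to comply with urine pregnancy testing requirements prior to initiation of trial testing procedures".
- Section 5.3, exclusion 4, second part: "any female subject of childbearing potential who fails to produce a negative urine pregnancy test".
- Section 6, screening procedures: "For female subjects of childbearing potential, a urine pregnancy test will be administered". Later in the same bullet: "A negative pregnancy result is required before any test material is applied to the subject".

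The first part of exclusion 4 does not depend on the term: "Female subject is pregnant or intending to become pregnant over the duration of the trial".

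Section 5.4.2 words the contraception duty for women differently: "female subjects who are of childbearing potential and are sexually active and at risk for pregnancy must agree". Here sexual activity and risk of pregnancy are added to childbearing potential and are not part of it.

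**The concern.** A definition that includes sexual activity suits a contraception duty, because a subject who is not sexually active has no need of contraception. It suits a screening test less well. Whether a woman is pregnant at screening depends on past intercourse, and inclusion 7 is in the present tense with no look-back period. One term serves both purposes, so a condition written for contraception also decides who must be tested.

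What is at stake is how a stated exclusion is enforced. The protocol does not appear to want pregnancy settled by report alone. Exclusion 5 marks lactation as self-reported, while exclusion 4 carries no such note and adds a urine test, for which Section 6 sets a sensitivity of at least 25 mIU/mL. A second issue is consistency: two staff members could each follow a part of the protocol and treat the same woman differently.

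**Working it through.** No arithmetic applies. The check is to trace the term through each provision that uses it, and to look for any baseline test requirement that does not depend on it.

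**Step 1: the definition.** Under inclusion 7, childbearing potential = biologically capable AND sexually active, both in the investigator's opinion.

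**Step 2: the test requirement.** Inclusion 8, the second part of exclusion 4 and the Section 6 screening bullet are each limited to female subjects of childbearing potential. No other text requires a baseline test. So test required = childbearing potential = biologically capable AND sexually active.

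**Step 3: the usage in Section 5.4.2.** The contraception duty for women applies if they are of childbearing potential AND sexually active AND at risk for pregnancy. If the first condition already contained the second, naming the second would be redundant. The natural reading is that childbearing potential there means biological capability.

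**Step 4: the two usages compared for a female subject.**

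| Subject | Test required, inclusion 7 meaning | Test required, Section 5.4.2 usage |
|---|---|---|
| Capable, judged sexually active | Yes | Yes |
| Capable, judged not sexually active | No | Yes |
| Not capable | No | No |

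The usages part only in the second row.

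**Step 5: what remains for the second row.** Section 6.2.1 gives every subject a provisional MEDu exposure within 1 week before the test material phase, and product application and further UV exposure follow. Under inclusion 7 this woman can go through both without a test. Four other provisions might reach her:

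- The ban on pregnant subjects in exclusion 4 still applies, but with no test it depends on what is known or reported.
- Section 6 includes a contraception check and an inquiry about changes in medical history, neither limited to childbearing potential. Both rest on what the subject says.
- Section 6 allows tests to be repeated on suspicion, at the IRB's request or if local regulations require. This is permissive, and it is described as a repeat, not a baseline test.
- The abstinence and same-sex-partner exemption in Section 5.4.2 concerns the list of contraceptive methods. It says nothing on testing.

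**Step 6: a bare deletion as remedy.** If the sexual-activity clause were simply struck from inclusion 7, the contraception sentence of that item would bind every biologically capable man and woman, including abstinent subjects. That would conflict with Section 5.4.2. The condition has to move to the contraception sentence.

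**The case against.** **The investigator decides.** The definition turns on the investigator's opinion, sets no time window and forbids no test. An investigator told of intercourse three weeks ago may well judge the woman sexually active and test her. This stands. A reader might infer that a woman who reports no sexual activity is automatically left untested; the text says only that a woman so judged is not required to be tested. The gap remains, because the investigator is asked to judge sexual activity, and a correct judgment that she is not sexually active still leaves no test required.

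**The negative-result sentence covers everyone.** It is worded generally, but it sits inside the bullet on female subjects of childbearing potential, and read literally for all subjects it would include men. At best it is ambiguous.

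**Section 5.4.2 gives no rival definition.** True. Its wording could be read as merely redundant, and for a woman who is sexually active and at risk both sections impose the same contraception duty. The difference for testing is an inference from usage. But even if Section 5.4.2 is read as redundant, inclusion 7 alone leaves the second row of the table without a required test.

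**Whom to test is the sponsor's decision.** It is. If testing is meant to be limited to sexually active women, the protocol can say so. As written, the limit comes in through a definition that another section uses differently.

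**Lost data.** A reader might infer that a missed pregnancy costs SPF results and uses up one of the 5 permitted exclusions. The documents do not support this. Section 6 expects the trial to last 3-10 days, so recognition within it would be needed. Section 8.9.2 keeps the data valid if pregnancy is discovered after participation. Section 7.1 does not list pregnancy as a ground for rejection; its example of withdrawal, under noncompliance, names illness or work conflicts.

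**Conclusion.** The point holds as a gap in safety screening and an inconsistency between Sections 5.2 and 5.4.2. Under inclusion 7, a fertile woman whom the investigator judges not sexually active need not be tested before UV exposure or application of product. Under the usage in Section 5.4.2 she would be. For her, exclusion 4 is enforced mainly through history and self-report.

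The size cannot be given from the documents. They state neither the sex split of the panel nor how many women would fall in this group. With a minimum of 10 valid subjects and a sponsor cap of 15 qualified subjects, the number may be zero. The documents also quantify no risk to a pregnancy.

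The SPF estimate, the ±17.0% confidence-interval criterion and the number of subjects are not affected. The conclusion rests on two readings: that the negative-result sentence in Section 6 is confined to its own bullet, and that Section 5.4.2 does not intend its added conditions as repetition. It is a cheap improvement to the wording, not a threat to the trial's result.

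**What to change.** Reconcile inclusions 7 and 8, exclusion 4, Section 5.4.2 and the Section 6 screening bullet so that childbearing potential has one meaning throughout. To match Section 5.4.2:

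1. In inclusion 7, remove sexual activity from the definition, leaving biological capability in the investigator's opinion.
2. In the contraception sentence of inclusion 7, add the two conditions that Section 5.4.2 already uses, being sexually active and being at risk for pregnancy. The contraception duty then stays as Section 5.4.2 states it and does not widen to abstinent subjects of either sex.
3. Leave inclusion 8, exclusion 4 and the Section 6 bullet as worded. With the term settled, they no longer depend on reported sexual activity.

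The cost is an edit to two sentences of one criterion, made through the amendment route of Section 11.6, and a few more urine dipsticks of the kind already used at screening. No analysis, sample-size or reporting text changes.

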### 5.3 Exclusion Criteria

1. Subject is in ill health as determined by the Principal Investigator;
2. Subject is an employee of the Clinical Division of the investigational site or a member of their immediate family;
3. Subject is a GSK CH employee directly involved in the conduct of the trial or a member of their immediate family;
4. Female subject is pregnant or intending to become pregnant over the duration of the trial or any female subject of childbearing potential who fails to produce a negative urine pregnancy test;
5. Female subject who is lactating (self-reported);
6. Subject using medication with photo-sensitizing potential;
7. Subject has a history of adverse reactions or hypersensitivity to azo dyes, cosmetics, OTC drugs, or other topical personal care products;
8. Subject taking medications other than birth control that could influence the purpose, integrity or outcome of the trial;
9. Subject has used topical or systemic steroids, antihistamines, or antibiotics within 7 days of trial initiation or during the trial;
10. Subject has used anti-inflammatory medications within 7 days of trial initiation or during the trial, that in the opinion of the PI, could interfere with the trial;
11. Subject has used medication suspected of causing photobiological reactions (e.g., tetracyclines, thiazides, etc.), that has not been taken by the subject through a summer season;
12. Subject has a dermatological condition;
13. Subject has a history of abnormal response to the sun, or a condition such as lupus erythematosus or skin cancer;
14. Subject uses tanning beds frequently;
15. Subject whose test site was exposed to sunlight within the previous 4 weeks;
16. Subject has a sunburn, suntan, uneven skin color, visible skin disease, scarring, or tattoo that would interfere with evaluation of test results;

Note: The presence of non-dysplastic nevi, blemishes, or moles will be acceptable if, in the PI's judgment, they will neither compromise the clinical trial, nor jeopardize a subject's safety. A subject with dysplastic nevi should be disqualified.

#### **CONFIDENTIAL**

This document is a confidential communication of Consumer Product Testing Company, Inc. containing Testing Facility capabilities and processes, and as such, is intended solely for the use of the Sponsor and Testing Facility in the performance of services. The confidential information contained herein, shall only be released by either Party upon compelled disclosure in compliance with legal or regulatory requirement.

17. Subject has existing sun damage in the test site;
18. Subject has excessive hair in the test area and are unwilling to have it clipped; or
19. Subject whose test sites have been used for clinical testing in which they were exposed to ultraviolet radiation within the past 2 months.

## **5.4 Lifestyle Considerations**

### **5.4.1 Medications and Treatments**

During the active trial period (screening through end of evaluation visit):

1. Subjects must not expose their backs to additional sunlight or a tanning bed, since exposure to either will alter response to the test.
2. Subjects must not apply any topical skin-care product to the test sites during this trial.

### **5.4.2 Contraception**

All male subjects able to father children and female subjects who are of childbearing potential and are sexually active and at risk for pregnancy must agree to use a highly effective method of contraception consistently and correctly for the duration of the active trial period and for 14 days after the last dose of investigational product.

The investigator or his or her designee will discuss with the subject the need to use highly effective contraception consistently and correctly according to the schedule of activities and document such conversation. In addition, the investigator or his or her designee will instruct the subject to call immediately if the selected contraception method is discontinued or if pregnancy is known or suspected in the subject or the subject's partner.

The following is the all-inclusive list of the highly effective methods for avoiding pregnancy that meets the GSK definition (i.e., have a failure rate of less than 1% per year when used consistently and correctly and, when applicable, in accordance with the product label).

The list does not apply to females of reproductive potential with same sex partners or for subjects who are and will continue to be abstinent from penile-vaginal intercourse on a long term and persistent basis, when this is their preferred and usual lifestyle. Periodic abstinence (e.g., calendar, ovulation, symptothermal, post-ovulation methods) and withdrawal are not acceptable methods of contraception (reference 12.3).

1. Contraceptive subdermal implant
2. Intrauterine device or intrauterine system

#### **CONFIDENTIAL**

This document is a confidential communication of Consumer Product Testing Company, Inc. containing Testing Facility capabilities and processes, and as such, is intended solely for the use of the Sponsor and Testing Facility in the performance of services. The confidential information contained herein, shall only be released by either Party upon compelled disclosure in compliance with legal or regulatory requirement.

3. Combined estrogen and progestogen oral contraceptive
4. Injectable progestogen
5. Contraceptive vaginal ring
6. Percutaneous contraceptive patches
7. Male partner sterilization with documentation of azoospermia prior to the female subject's entry into the trial, and this male is the sole partner for that subject. The documentation on male sterility can come from site personnel review of subject's medical records, medical examination and/or semen analysis, or medical history interview provided by her or her partner.

Male subjects with female partners of child-bearing potential must comply with the following contraception requirements from the time of first dose of trial medication until 14 days after the last dose of trial medication.

1. Vasectomy with documentation of azoospermia. The documentation on male sterility can come from site personnel: review of subject's medical records, medical examination and/or semen analysis, or medical history interview.
2. Male condom plus partner use of one of the contraceptive options below that meets the effectiveness criteria including a <1% rate of failure per year, as stated in the product label:
  - Contraceptive subdermal implant
  - Intrauterine device or intrauterine system
  - Combined estrogen and progestogen oral contraceptive
  - Injectable progestogen
  - Contraceptive vaginal ring
  - Percutaneous contraceptive patches

These allowed methods of contraception are only effective when used consistently, correctly and in accordance with the product label. The investigator is responsible for ensuring that subjects understand how to properly use these methods of contraception.

## 5.5 Withdrawal of Subjects

The subject is free to withdraw their consent to participate in the trial at any time and for any reason, in accordance with the Principles of the World Medical Association Declaration of Helsinki (as amended). The PI also has the right to withdraw a subject from the trial for safety, lack of efficacy, or administrative reasons.

Possible reasons why a subject may be withdrawn from the trial include the following:

1. Experiences an AE or SAE;
2. Develops, during the trial, symptoms or conditions listed in the exclusion criteria, including hypersensitivity to the test material or pregnancy;
3. Takes medications that are contraindicated, as described in the exclusion criteria;
4. Incurs a protocol violation such as failure to comply with the specified treatment regimen or failure to comply with the visit schedule; or

